# 8.2.2 Imputation of Adverse Event start dates

To assess if AEs are treatment emergent, missing onset dates will be imputed according to the following rules:

- If day is missing and month and year of AE onset is the same as the month and year of first dose of study treatment, then the onset date of the AE will be assumed to be the same as the date of first dose of study treatment.
- If day and month is missing and year of AE onset is the same as year of first dose, then the date of onset will be assumed to be the same as the first dose of study treatment.
- Otherwise, if day is missing, then use YYYY-MM-01, and if day and month are missing, then use YYYY-JAN-01.
- Completely missing onset dates will not be imputed. AEs with a completely missing onset date will be considered treatment-emergent.

### 8.2.3 Imputation of prior/concomitant medication start/stop date

To assess if medications are prior or concomitant, missing onset dates will be imputed according to the following rules:

- If day is missing and month and year are both available, use 01 of the month or the date of first dose of study treatment whichever is later.
- If only the year is available, use 01 Jan of the year or the date of first dose whichever is later.
- Completely missing onset dates will not be imputed.

Likewise, to assess if a medication is prior, missing stop dates will be imputed according to

- If the day is missing: Assume the last day of the month.
- If the month is missing: Assume 31 Dec of the year.
- Completely missing stop dates will not be imputed

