6.3.1 Inclusion criteria

A patient must fulfill all of the following criteria in order to be included in the study:

1. Signed informed consent.
2. Male and female patients with a body weight ≥ 10 kg.
3. Diagnosis of Still's disease:
 - a. If < 16 years of age at disease onset, according to adapted ILAR criteria i.e., CARRA-criteria for SJIA. See Appendix 1.
 - b. If ≥ 16 years of age at disease onset, according to Yamaguchi criteria. See Appendix 1.
4. If currently on glucocorticoid treatment, a stable dose for at least 1 week prior to randomization. Maximum dose allowed is 1 mg/kg/day, up to a maximum of 60 mg/day.
5. If currently on methotrexate treatment, a stable dose for at least 8 weeks prior to randomization. Maximum dose allowed is 20 mg/m²/week. If prior treatment with methotrexate, discontinuation is required to be at least 4 weeks prior to randomization.
6. Active disease confirmed by the following three signs and symptoms:
 - a. Active arthritis in ≥ 1 joint
 - b. CRP > 30 mg/L
 - c. At least one fever episode attributable to the disease within one week before randomization.
(Definition of fever: body temperature $\geq 38.0^{\circ}\text{C}$)
7. Female patients of childbearing potential must use an effective method of contraception during the study (abstinence being a possible option) as well as present a negative pregnancy test prior to randomization.
8. Negative interferon-gamma release assay or PPD test within 2 months prior to randomization. If not available, a test should be performed at day of randomization (see 6.5.5.6.1).

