6.5.1.1 Screening visit (optional)

The screening may be done at a separate visit before the baseline visit to identify patients that could be suitable for the study and/or to ensure that required lab results are available before randomization (see 6.5.5.6.1). Applicable ICFs must be obtained prior to any screening

activities (see 2.3). Once the ICF has been signed, the patient will be assigned an enrolment number.

Any SAE that occur after the informed consent has been signed must be reported (see 6.5.5.1.4).

6.5.1.2 Baseline visit, Day 1

If a screening visit has not been performed applicable ICFs must be obtained prior to any study related activities. Once the ICF has been signed, the patient will be assigned an enrolment number.

Any SAE that occur after the informed consent has been signed must be reported.

All inclusion and exclusion criteria should be reviewed (see 6.3) to assess patient's eligibility. The laboratory tests that are needed for evaluation of inclusion and exclusion criteria should be performed before randomization (see 6.5.5.6.1). If it is expected that any of the lab results are not available within reasonable time a screening visit should be performed the day before (the eligibility laboratory results are valid for 36 hours). See 6.5.1.1. However, a patient can be randomized before results from a interferon-gamma release assay or a PPD test has been confirmed. If the results from this test is positive, that is not due to vaccination (PPD), the patient must be withdrawn from the study (see 6.3.3).

Data will be collected on medical history (see 6.5.2), demographics (see 6.5.3) and prior and concomitant medication (see 6.4.6). Vital signs (see 6.5.5.2) and physical examination (see 6.5.5.3) will be performed.

If the patient has been found eligible, the patient will be randomized .

As part of ACR the physician global assessment of disease activity, patient or parent global assessment of overall well-being, the patient or parent assessment of physical function, assessment of number of joints with active arthritis and number of joints with limited range of motion will be assessed (see 6.5.4.1). Global assessment of the patient disease related pain (see 6.5.4.2), and a 12-lead ECG (see 6.5.5.4) will be assessed.

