Prior to the first IMP administration, blood samples will be collected for central laboratory assessments (see 6.5.5.6.2) immunogenicity assessments (see 6.5.5.5), IL-1Ra/anakinra serum concentration assessments (see 6.5.6) and exploratory inflammatory biomarkers (see 6.5.7). For patients consenting to pharmacogenetic assessment an additional blood sample will be collected at a suitable visit after randomization (see 6.5.7.2).

Finally, the first dose of IMP is to be administered and the time point of administration will be recorded. The patient or patient's caregiver will be instructed how to administer the IMP dose on a daily basis and how to complete the diary (see 9.2) and IMP covering the period until next visit will be dispensed.

Adverse events, will be recorded from the time of the first IMP administration (see 6.5.5.1).

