#### 11 Prior and concomitant medication

All prior and concomitant medication will be coded using the WHO Drug dictionary.

The preferred term grouped by ATC level 4 will be used for presentation and sorted in descending order of frequency in total (both treatment groups together) at the top in the table.

Prior medication, concomitant medication at randomization and onset of new concomitant medication after randomization during the study will be summarized separately for both the mITT set and the Safety set.

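### SAP 8.2.3 moves every partial medication start date that begins before first dose to the first-dose date, even when the recorded month or year rules that date out

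*SAP*

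**What the plan says.** SAP 8.2.3 imputes partial medication dates in order to class drugs as prior or concomitant.

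- **Start, day missing:** "use 01 of the month or the date of first dose of study treatment whichever is later".
- **Start, only the year known:** "use 01 Jan of the year or the date of first dose whichever is later".
- **Start completely missing:** left missing.
- **Stop:** "to assess if a medication is prior, missing stop dates will be imputed according to" a separate rule, which takes the last day of the month or 31 December. It is not linked to the start date.

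SAP 8.2.2 handles partial adverse event onsets differently. With the day missing, it uses the first-dose date only if "month and year of AE onset is the same as the month and year of first dose of study treatment". If the month is missing too, only the year has to match. In all other cases it keeps the recorded period and takes its first day.

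SAP 11 presents three medication summaries: prior medication, medication at randomization, and a third in which "onset of new concomitant medication after randomization during the study will be summarized separately". It gives no date comparison to separate the last two.

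**The concern.** Assuming the first-dose date is a sensible convention when a partial date is ambiguous, that is, when the recorded month or year contains first dose. SAP 8.2.3 also applies it when the recorded month or year shows that the drug began earlier. Under this rule no partial start can ever fall before first dose, although the rule exists to help separate prior from concomitant drugs. A completely missing start stays missing, so a record with more information gets a date which that information contradicts.

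Such records are plausible here because the protocol allows background treatment. Its entry criterion reads "If currently on methotrexate treatment, a stable dose for at least 8 weeks prior to randomization", so that dose always began in an earlier calendar month. Protocol 6.4.6 prohibits starting continuous NSAIDs during the study, and an NSAID taken since before entry with a partial start date would appear to begin on Day 1. A compliant patient could then look non-compliant in the imputed data.

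At stake is whether background drugs are reported as present at randomization or as newly started after it.

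**Working it through.** The plan gives no figure on this point. The check applies the stated rules to dates. All calendar dates below are assumptions chosen for illustration.

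**1. General result.** Let F be the first-dose date and P the first day of the recorded month or year. SAP 8.2.3 gives imputed start = max(P, F). If P < F, this is always F. If the drug stopped at S < F, the imputed start F is later than S.

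**2. Enumeration.** The rules were run over 48 first-dose dates in 2018 (12 months × days 1, 10, 15 and 28).

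| Case | Count | Result |
|---|---|---|
| Day missing, each of 24 earlier months | 48 × 24 = 1,152 | 1,152 set to F |
| Year only, each of 3 earlier years | 48 × 3 = 144 | 144 set to F |
| Earlier start month, stop month also before that of F | 48 × (1 + … + 24) = 14,400 | 14,400 with start after stop |

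On the same 1,152 earlier-month starts, the SAP 8.2.2 logic kept all 1,152 before first dose.

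**3. Size of the date error, with F = 10 July 2018.**

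| Recorded start | Imputed under 8.2.3 | Error |
|---|---|---|
| March 2018 | max(1 March, 10 July) = 10 July 2018 | 101 to 131 days late |
| June 2018 | max(1 June, 10 July) = 10 July 2018 | 10 to 39 days late |
| 2017 | max(1 Jan 2017, 10 July 2018) = 10 July 2018 | 191 to 555 days late |

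Under the 8.2.2 logic the March record becomes 1 March, which is 0 to 30 days early. If that drug stopped on 20 May 2018, the 8.2.3 start falls 51 days after the stop (20 May to 10 July).

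**4. Methotrexate.** Eight weeks is 56 days and no month exceeds 31 days, so a dose stable for 8 weeks always began in an earlier calendar month than Day 1. If only the day is missing, it is dated to Day 1, at least 56 days late.

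**5. Effect on the SAP 11 tables.** At the Day 1 visit (Protocol 6.5.1.2), "If the patient has been found eligible, the patient will be randomized", and later in that visit "the first dose of IMP is to be administered and the time point of administration will be recorded". The imputed start therefore equals the randomization date, exactly on the boundary between two tables.

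- If new onset means start later than the randomization date, the drug stays in the at-randomization table and the shift is 0.
- If it means on or after that date, the drug moves to new onset. The table shows the shift from one patient who was not already in that row.

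| Total N, 2:1 allocation | Placebo | Anakinra |
|---|---|---|
| 12 (SAP 4.2 minimum) | 1/4 = 25.0 points | 1/8 = 12.5 points |
| 24 (assumed) | 1/8 = 12.5 points | 1/16 = 6.3 points |

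**6. Is the 8.2.2 logic enough on its own?** Not quite. Take a year-only start of 2018, a stop of July 2018 and first dose on 15 September 2018. The year matches, so the start becomes 15 September 2018 while the stop is imputed as 31 July 2018. A limit at the drug's own stop date is also needed.

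**The case against.** The best reply is that no table need change. In ordinary language, onset after randomization excludes the randomization date, so a drug imputed to Day 1 stays in the at-randomization table. Drugs that stopped before first dose are still classed as prior through the stop-date rule, and ongoing drugs are concomitant whichever start is imputed. SAP 11 computes no durations, so a start after a stop alters no reported result. Nothing says the recorded partial date is discarded, and sites must establish methotrexate timing for eligibility anyway.

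Much of this stands. The prior classification by stop date survives, the frequency of partial dates is unknown and may be zero, and the day counts measure date error rather than error in a reported result.

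The reading of *after* is not secure, however. SAP 13.2 defines a treatment-emergent event as one starting after first administration, yet SAP 8.2.2 moves ambiguous onsets to the first-dose date in deciding whether they are treatment-emergent. If those events are meant to count, the SAP itself places that date on the *after* side. A programmer who follows the same convention for medications would put background drugs among the new onsets.

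**Conclusion.** The concern holds. SAP 8.2.3 as written assigns dates that the recorded month or year contradicts, and it can place a start after the drug's own stop. This follows from the wording alone and needs no assumption about the data.

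The consequence is limited and conditional. It is confined to the descriptive medication tables; no primary or key secondary analysis uses these dates. Under an on-or-after cut-off, each misplaced patient shifts a row by 25.0 points (placebo) or 12.5 points (anakinra) at 12 patients; under a strictly-after cut-off the shift is zero. The documents do not settle which applies, nor how many records are affected. The rule should be corrected because it is wrong as stated, but it does not threaten the trial's efficacy conclusions.

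**What to change.** In SAP 8.2.3, adopt the 8.2.2 condition with a stop-date limit:

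- Impute the first-dose date only when the known month and year (or the year, if the month is missing) equal those of first dose and the stop date does not show that the drug ended earlier.
- Otherwise use the first of the known month, or 1 January of the known year.
- Never impute a start later than the drug's stop date.

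In SAP 11, state the date comparison that separates medication at randomization from onset after randomization. This is needed even with the revised rule, because ambiguous starts in the month or year of first dose still land on Day 1.

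The cost is two lines of wording in 8.2.3, one in SAP 11 and the matching code, with no data change. It should be done before the SAP is locked, which SAP 5.2 places before database lock and unblinding.

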### 8.2.4 Imputation of date of disease diagnosis

Missing dates for the diagnosis of Still's disease will be imputed according to the following rules:

• If day is missing, the day will be imputed as the 15th, i.e. YYYY-MM-15, in the calculation.

- If the month is missing, it will be imputed as June, i.e. YYYY-06-15
- Completely missing date will not be imputed

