6.3.2 Exclusion criteria

The presence of any of the following will exclude a patient from inclusion in the study:

1. Diagnosis of Still's disease more than 6 months prior to randomization.
2. Previous randomization into this study
3. Participation in another concurrent clinical interventional study within 30 days of randomization.
4. Treatment with an investigational drug within 5 half-lives prior to randomization.
5. Previous or current treatment with anakinra, canakinumab or any other IL-1 inhibitor.
6. Use of the following therapies prior to randomization:
 - Narcotic analgesics within 24 hours prior to randomization
 - Dapsone or etanercept within 3 weeks prior to randomization
 - Intraarticular, intramuscular or intravenous administration of glucocorticoids or intravenous Ig within 4 weeks prior to randomization
 - Intravenous Ig with proven Still's disease modifying effect, leflunomide, infliximab, or adalimumab within 8 weeks prior to randomization

- Thalidomide, cyclosporine, mycophenolate mofetil, 6-mercaptopurine, azathioprine, cyclophosphamide, chlorambucil, or any other immunosuppressant within 12 weeks prior to randomization
 - Tocilizumab within 12 weeks prior to randomization or any other immunomodulatory medication within 4 half-lives prior to randomization
 - Rituximab within 26 weeks prior to randomization
7. Live vaccines within 1 month prior to randomization.
 8. Known presence or suspicion of active, chronic or recurrent bacterial, fungal or viral infections, including tuberculosis, HIV infection or hepatitis B or C infection.
 9. Clinical evidence of liver disease or liver injury as indicated by presence of abnormal liver tests
 - AST or ALT >5 x ULN, *or*
 - AST or ALT >3 x ULN accompanied by elevated bilirubin >2 x ULN.
 10. Presence of severe renal function impairment CKD stages 4 and 5 (estimated creatinine clearance < 30 mL/min/1.73m²).
 11. Presence of neutropenia (ANC < 1.5 x 10⁹/L).
 12. Presence or suspicion of MAS at baseline. (See Appendix 2 for guidance).
 13. A diagnosis of MAS within 2 months prior to randomization.
 14. History of malignancy within 5 years. Exceptions are basal cell skin cancer, carcinoma-in-situ of the cervix or low-risk prostate cancer after curative therapy.
 15. Known hypersensitivity to E coli-derived proteins, or any components of Kineret (anakinra).
 16. Pregnant or lactating women.
 17. Foreseeable inability to cooperate with given instructions or study procedures.

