# 4.2 Selection of study population

A total of 81 patients was originally planned to be randomized, but fewer patients are expected since recruitment will be stopped earlier. At least 12 patients are expected to be randomized, with a 2:1 allocation (anakinra:placebo).

For inclusion into the study, a patient should have active Still's disease, diagnosed not more than 6 months prior to randomization. Diagnosis of Still's disease:

- a) If < 16 years of age at disease onset, according to adapted ILAR criteria i.e., CARRAcriteria for SJIA.
- b) If  $\geq 16$  years of age at disease onset, according to Yamaguchi criteria.

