#### 8.5.5 Primary disease characteristics

Age at Still's disease diagnosis will be calculated based on date of birth and the date of Still's disease diagnosis as recorded on the Demography eCRF form.

Disease duration will be derived based on the Day 1 visit date and the date of Still's disease diagnosis, as recorded on the Demography eCRF form.

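### The imputation rule for partial diagnosis dates has no limit at Day 1, so it can give a negative disease duration

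*SAP*

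**What the plan says.** SAP section 8.2.4 has three rules for an incomplete date of diagnosis:

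- Day missing: "If day is missing, the day will be imputed as the 15th, i.e. YYYY-MM-15, in the calculation".
- Month missing: "If the month is missing, it will be imputed as June, i.e. YYYY-06-15".
- Whole date missing: "Completely missing date will not be imputed".

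None of them refers to Day 1 or randomization, and no such limit appears elsewhere in the SAP or the protocol.

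Two variables use the date. SAP section 8.5.5 states: "Disease duration will be derived based on the Day 1 visit date and the date of Still's disease diagnosis". It also states that age at Still's "disease diagnosis will be calculated based on date of birth and the date of Still's disease diagnosis". SAP section 10.3 summarizes both, together with age at symptom onset, for the mITT and Safety sets.

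On timing, SAP section 4.2 describes the population as "diagnosed not more than 6 months prior to randomization", and exclusion criterion 1 (Protocol section 6.3.2) rules out a diagnosis of Still's "disease more than 6 months prior to randomization". Randomization takes place at the Day 1 visit (Protocol section 6.5.1.2).

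**The concern.** A diagnosis is an entry requirement, so it cannot be later than Day 1. Diagnosis is also recent in this trial, so Day 1 often falls in the same month or year as the diagnosis. A mid-month or mid-year default then has a real chance of landing after Day 1.

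The two preceding sections of the SAP, on onset dates of adverse events (8.2.2) and medications (8.2.3), tie their imputed dates to first dose. The diagnosis rule has a natural limit of the same kind and does not use it.

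At stake is the baseline description of how recent the disease is. The SAP expects at least 12 patients randomized 2:1, which is about 8 on anakinra and 4 on placebo. One impossible value would show in the minimum and move the mean and SD.

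**Working it through.** The documents give no figure for this rule, so there is nothing of the plan's own to reproduce. The check applies the rule to calendar dates, with duration = Day 1 minus imputed diagnosis date.

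**Worked dates, Day 1 on 06-Mar-2018**

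- Recorded as March 2018: imputed 15-Mar-2018. Duration = 6 - 15 = -9 days.
- Recorded as 2018: imputed 15-Jun-2018. From 06-Mar to 15-Jun is 25 + 30 + 31 + 15 = 101 days, so duration = -101 days.

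**Where the rule must fail.** If Day 1 is between 1 January and 14 June and the diagnosis is in the same year with the month missing, the imputed 15 June is always after Day 1. The result runs from -165 days (Day 1 on 1 January) to -1 day (14 June). This needs no assumption about how durations are distributed.

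**How often, given a partial date.** Take every Day 1 in 2019 and every true diagnosis date from six calendar months before Day 1 up to Day 1, equally weighted. That makes 66,981 pairs. The equal weighting is an assumption.

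- Month missing: when Day 1 is the k-th day of the year (k = 1 to 165), there are k same-year diagnosis dates and all give a negative result. The sum is 165 × 166 / 2 = 13,695, and 13,695 / 66,981 = 20.4%.
- Day missing: when Day 1 is the d-th of a month (d = 1 to 14), there are d same-month diagnosis dates and all give a negative result. The sum is 14 × 15 / 2 = 105 per month, or 1,260 per year, and 1,260 / 66,981 = 1.9%. The lowest value is -14 days.

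**Sensitivity to the assumed spread.** Shorter true durations raise both shares:

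| True duration (uniform) | Pairs | Day missing, negative | Month missing, negative |
|---|---|---|---|
| up to 6 months | 66,981 | 1,260 = 1.9% | 13,695 = 20.4% |
| 0 to 30 days | 365 × 31 = 11,315 | 1,260 = 11.1% | 465 + 31 × 135 = 4,650 = 41.1% |
| 0 to 14 days | 365 × 15 = 5,475 | 1,260 = 23.0% | 105 + 15 × 151 = 2,370 = 43.3% |

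The documents do not say that durations are this short. The lower rows only show the range.

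**Effect of one bad value.** With Day 1 on 06-Mar-2018 and a diagnosis in 2018, the true duration lies between 0 and 64 days (1 January to 6 March). Imputing -101 therefore understates it by 101 to 165 days. In a group of 8 the mean duration is too low by 101/8 = 12.6 to 165/8 = 20.6 days, whatever the other seven values are. Age at diagnosis for that patient is too high by 101/365 = 0.3 to 165/365 = 0.5 years.

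**The case against.** **It may never happen.** The rule acts only on partial dates. Sites have to check the 6-month limit at entry, so a missing month should be rare for a recent diagnosis. For a missing day, even if all 12 patients lacked it, the expected number of negative values under the even spread is 12 × 1.9% = 0.2. This stands and sets the size of the point. It does not rescue the rule, which was written for exactly these records.

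**The effect is only descriptive.** Disease duration and age at diagnosis appear in a baseline summary. They do not enter the primary test (SAP 12.1) or the stratification, which uses age at onset (SAP 4.3), and there are no subgroup analyses (SAP 12.5). The median is reported as well, and one outlier barely moves it. All of this stands.

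**A stronger reading is tempting.** The same enumeration puts 29.3% of month-missing and 2.3% of day-missing imputations more than 6 months before Day 1. For example, a diagnosis recorded as 2017 with Day 1 on 20-Jan-2018 becomes 15-Jun-2017, which is 219 days. A reader might add these to the negative values, call about half of month-missing imputations impossible, and infer that the rule makes patients ineligible. The documents do not support that. Exclusion criterion 1 is judged at entry, and the only exclusions from the mITT set (SAP 7.4) are failure of the ILAR or Yamaguchi criteria and receiving no IMP, so an imputed date reclassifies nobody. Nor is such a value impossible. It lies within the recorded month or year, so the record itself leaves open a diagnosis outside the limit. That is a matter for a data query, not an imputation error.

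**Conclusion.** The concern holds in a limited form. If a partial diagnosis date is recorded, SAP 8.2.4 can date the diagnosis after enrolment and produce a negative disease duration, and nothing else in the plan corrects it. Only negative values are impossible: about 20% of month-missing and 2% of day-missing imputations, if true durations are uniform over six months and enrolment is even over the year. The number of partial dates is unknown and may be zero.

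The consequence is confined to the descriptive summaries of disease duration and, slightly, age at diagnosis. Eligibility, analysis sets and efficacy tests are untouched. The correction is desirable but not essential.

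**What to change.** Cap the imputed diagnosis date in SAP 8.2.4 at Day 1. One form: use the midpoint, rounded down, between the start of the recorded month or year and the earlier of its end or Day 1. By construction this is never after Day 1. For Day 1 on 06-Mar-2018:

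- March 2018: 1 to 6 March, midpoint 3 March, duration 3 days instead of -9.
- 2018: 1 January to 6 March is 64 days, midpoint 2 February, duration 32 days instead of -101.

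Add one sentence on queries. If the imputed date falls more than 6 months before randomization, or the recorded period begins after Day 1, ask the site for the full date. Do not force the date into the 6-month window. That would assume eligibility, could hide a true deviation from exclusion criterion 1, and is undefined when the recorded period does not overlap the window. The 2017 record with Day 1 on 20-Jan-2018 shows the working: the midpoint is 2 July 2017, or 202 days, so it is queried.

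The cost is about two lines of SAP text, a matching change in the derivation code, and possibly a few site queries before database lock. No collected data change.
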